6.8.3. Health State Utility

The EQ-5D 5L data will be scored as described by van Hout et al. (van Hout et al. 2012). The index score is calculated from a set of item weights to derive a score of 0 to 1, with 1 representing the best health status. Geographic-specific weights will be used as appropriate and when available. The Visual Analog Scale (VAS) is scored from 0 (*worst imaginable health state*) through 100 (*best imaginable health state*) to represent the patient's self-report for each day. The EQ-5D 5L responses for each item will be summarized by frequency and corresponding percentages. Descriptive statistics for the index and VAS will be calculated by arm and cycle. Psychometric analyses, including calculation of reliability coefficients (Cronbach's alpha), will also be performed.

For both the index score and VAS, a mixed effects, repeated measures model will be applied to compare treatment arms by cycle. The model will include baseline score as a covariate and an unstructured covariance matrix will be utilized. The analysis will include all cycles for which at least 25% of patients in each arm have an assessment.

6.8.4. Utilization

Utilization data will be summarized by category across arms. The following categories will be described:

- analgesics (on study treatment and during short term follow up)
- transfusions (on study treatment and during short term follow up)

- surgery (on study treatment and during short term follow up)
- hospitalizations (on study treatment and during short term follow up)
- post discontinuation radiotherapy and systemic therapy.

For categorical variables, frequency and the corresponding proportions will be calculated and tests for differences in proportion between groups will be performed using a chi-squared test. Continuous variables will be described by the mean, median, and standard deviation. A t-test will be used to compare mean utilization.

6.9. Bioanalytical and Pharmacokinetic/Pharmacodynamic Methods

Pharmacokinetic and pharmacodynamic analyses will be performed according to a separate PK analysis plan.

6.10. Tailoring Biomarker Analyses

The distributions of biomarkers with continuous measures, such as gene or protein expression, will be described. Summary statistics will include means, medians, corresponding standard errors, quartiles, and ranges. Biomarkers with discrete measures, such as genotype locus, will be summarized in frequency tables. Correlative analyses may be performed to investigate associations between biomarkers and clinical endpoints as deemed appropriate.

Further analysis of biomarkers will be described in a separate biomarker SAP.

6.11. Safety Analyses

6.11.1. Extent of Exposure

For blinded study drug, extent of exposure will be measured by pill counts and summarized cumulatively. The summary will include total dosage taken and dose intensity. Dose intensity will be calculated as the ratio of total dose taken to the assigned cumulative dose. The assigned cumulative dose for each patient during each cycle is $150 \text{ mg per dose} \times 2 \text{ doses per day} \times 28 \text{ days} = 8400 \text{ mg}$. The assigned cumulative dose while on study is $2 \times 150 \text{ mg} \times \text{number of days on treatment}$.

For co-administered NSAID, extent of exposure will be measured based on pill count data (for those sites using Lilly supplied NSAID) or data reported on 'Exposure Compliance: NSAID' form (for those sites using locally supplied NSAID), and summarized cumulatively. The summary will include total doses taken and dose intensity. Dose intensity will be calculated as the ratio of total doses taken to the assigned number of doses. The assigned number of doses for each patient during each cycle is $1 \text{ dose per day} \times 28 \text{ days} = 28 \text{ doses}$. The assigned number of doses while on study is $1 \text{ dose per day} \times \text{number of days on treatment}$.

Dose adjustments and omissions, along with the reason for adjustment or omission, will be summarized for blinded study drug and NSAID.

6.11.2. Adverse Events

Adverse event (AE) terms and severity grades will be assigned by the investigator using Common Terminology Criteria for Adverse Events (CTCAE) Version 4. In addition, AE verbatim text will also be mapped by the sponsor or designee to corresponding terminology within MedDRA. Adverse events will be reported using the following reporting process:

- The CTCAE Version 4 term reported by the investigator will be mapped to the MedDRA PT and system organ class (SOC) of the corresponding MedDRA lower level term (LLT), unless the reported CTCAE term is ‘Other – specify’.
- If the reported CTCAE term is ‘Other – specify’ the MedDRA LLT, PT and SOC mapped from the verbatim AE term will be used.
- Preferred terms identified by Medical as clinically identical or synonymous will be grouped together under a single consolidated PT. For example, ‘Asthenia’ and ‘Fatigue’ will be reported as ‘Fatigue.’ See [Appendix 1](#) for a complete listing. This listing may be updated prior to database lock as new synonymous terms are observed.
- All listings and summaries will use the PT resulting from this process.

Pre-existing conditions are defined as AEs that begin prior to the first dose of study drug.

A treatment emergent adverse event (TEAE) is defined as any AE that begins between the day of first dose and 30 days after treatment discontinuation (or up to any time if serious and related to study treatment), or any pre-existing condition that increases in CTCAE grade between the day of first dose and 30 days after treatment discontinuation (or up to any time if serious and related to study treatment). Comparisons of pre-existing conditions to on-treatment events at the LLT level will be used in the treatment-emergent computation.

A serious adverse event (SAE) is any AE during this study that results in one of the following outcomes:

- death
- initial or prolonged inpatient hospitalization
- a life-threatening experience (that is, immediate risk of dying)
- persistent or significant disability/incapacity
- congenital anomaly/birth defect
- considered significant by the investigator for any other reason.

Important medical events that may not result in death, be life-threatening, or require hospitalization may be considered SAEs when, based on appropriate medical judgment, they may jeopardize the patient and may require medical or surgical intervention to prevent one of the outcomes listed in this definition.

To assess the relationship of the AE to the study treatment, the following terminologies are defined (in Protocol Section 8.1.2):

- **Related:** a direct cause and effect relationship between the study treatment and the AE is likely.
- **Possibly related:** a cause and effect relationship between the study treatment and the AE has not been demonstrated at this time and is not probable, but is also not impossible.
- **Unrelated:** without question, the AE is definitely not associated with the study treatment.

As per Lilly's standard operating procedures (SOPs), all "related" and "possibly related" AEs and SAEs will be defined as related to study treatment.

The following TEAE/SAE listings and summaries will be produced:

- Overview of TEAEs
- Summary of TEAEs by PT (all grade and grade ≥ 3)
- Summary of TEAEs by SOC and PT (all grade and grade ≥ 3)
- Summary of TEAEs by PT and maximum grade (1-5)
- List of SAEs
- Summary of SAEs by SOC and PT (all grade and grade ≥ 3).

The four summaries will be produced for all TEAEs/SAEs and repeated for TEAEs/SAEs related to study treatment.

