10.3.1. Adverse Events

Lilly has standards for reporting AEs that are to be followed regardless of applicable regulatory requirements that may be less stringent. A clinical study AE is any untoward medical event associated with the use of a drug in humans, whether or not it is considered related to that drug.

Lack of drug effect is not an AE in clinical trials, because the purpose of the clinical trial is to establish drug effect.

Any clinically significant findings from ECGs, labs, vital sign measurements, and other procedures that result in a diagnosis should be reported to Lilly or its designee.

Study site personnel will record the occurrence and nature of each patient's preexisting conditions, including clinically significant signs and symptoms of the disease under treatment in the study.

After the ICF is signed, site personnel will record the occurrence and nature of any AEs and any change in the preexisting condition(s). All AEs related to protocol procedures are reported to Lilly or its designee.

Investigators will be instructed to report to Lilly or its designee their assessment of the potential relatedness of each AE to protocol procedure and study drug via eCRF.

The investigator will decide whether he or she interprets the observed AEs as related to disease, to the study medication, study procedure, or other concomitant treatment or pathologies. To assess the relationship of the AE to the study drug or procedure, the following terminologies are defined:

- **Probably related**: a direct cause and effect relationship between the study treatment and the AE is likely
- **Possibly related**: a cause and effect relationship between the study treatment and the AE has not been demonstrated at this time and is not probable, but is also not impossible
- **Does not know:** the investigator cannot determine
- **Not related**: without question, the AE is definitely not associated with the study treatment

The investigator should classify all "probably related," "possibly related," or "does not know" AEs and SAEs as related to study drug/study procedure.

Patients will be evaluated for AEs at each visit and will be instructed to call their physician to report any AEs between visits.

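### SAP 6.11.2 gives the protocol's *does not know* category no mapping, so events the protocol counts as treatment-related could drop out of the related summaries

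*SAP*

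**What the plan says.** Protocol 10.3.1 asks investigators to report their "assessment of the potential relatedness of each AE to protocol procedure and study drug via eCRF". It defines four categories: probably related, possibly related, does not know, and not related. *Does not know* is a category of its own, for events where "the investigator cannot determine". The investigator is then told to classify the first three kinds of "AEs and SAEs as related to study drug/study procedure".

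SAP 6.11.2 says that, for relatedness, "the following terminologies are defined (in Protocol Section 8.1.2". It lists three: related, possibly related and unrelated. It then invokes the sponsor's standard operating procedures and states that related and possibly related "AEs and SAEs will be defined as related to study treatment". *Does not know* does not appear.

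The definition is used twice in the same SAP section:

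- The TEAE and SAE summaries are produced for all events and repeated for related events.
- The TEAE window closes 30 days after treatment discontinuation, "or up to any time if serious and related to study treatment". The same exception applies to pre-existing conditions that worsen in grade.

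**The concern.** The two documents state different rules for the same quantity, and the SAP presents its list as the protocol's own. The protocol's rule is the cautious one: where the investigator cannot decide, the event counts against the treatment. The SAP's rule contains no such step.

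Two outputs are at stake. The first is the set of related TEAE and SAE summaries. The second is the TEAE status of late serious events. In long-term follow-up the protocol collects only SAEs related to protocol procedures or study drug (Table JPBM.10.3). A late serious *does not know* event could therefore be collected because the protocol treats it as related, and then fail to be a TEAE because the SAP does not.

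The cross-reference adds to the doubt. In the supplied protocol, Section 8.1.2 is the Continued Access Period and holds no relatedness definitions.

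**Working it through.** The plan states no figure to reproduce. The check compares the two lists and then follows the SAP's rule to its outputs.

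**1. The categories side by side**

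| Protocol 10.3.1 | Counts as related? | SAP 6.11.2 | Counts as related? |
|---|---|---|---|
| Probably related (causal link likely) | Yes | Related (same definition) | Yes |
| Possibly related (not shown, not probable, not impossible) | Yes | Possibly related (same definition) | Yes |
| Does not know | Yes | No entry | No rule |
| Not related (certain) | No | Unrelated (same definition) | No |

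Three of the four rows agree in substance. *Probably related* changes its label only. The single real difference is the third row.

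**2. Whether the SAP catches the third row elsewhere**

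- *Unrelated* requires certainty that there is no association, so an undetermined event does not meet that definition.
- By label, it is neither *related* nor *possibly related*. The protocol keeps it apart from *possibly related*.
- SAP 6.2 imputes nothing except dates, so no default turns an undetermined or missing value into related.

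A program that selects the two named values would leave *does not know* out.

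**3. Whether the change is declared**

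Protocol 12.2.1 lets the SAP make minor modifications before unblinding if they are described and justified. SAP Section 8 reports no significant changes for Versions 1 to 3 and has no entry for Versions 4 and 5. The revision history in SAP Section 3 mentions a clarified TEAE definition but no change to relatedness categories.

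**4. Size**

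Let P, Q and D be the numbers of events recorded as probably related (the SAP's related), possibly related and does not know.

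- Related under the protocol: P + Q + D
- Related under the SAP, applied literally: P + Q
- Relative fall: D/(P + Q + D)

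The fall is zero if D = 0 and positive otherwise. The documents give no value for D.

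The denominator matters when reading this. If a share d of all AEs is *does not know*, and a share R of all AEs is related under the protocol's rule, the fall is d/R. Since R cannot exceed 1, that is at least d. For illustration only, with every input assumed:

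- d = 5%, R = 50%: 0.05/0.50 = 10%
- d = 10%, R = 50%: 0.10/0.50 = 20%
- d = 10%, R = 60%: 0.10/0.60 = about 17%

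These are falls in event counts. Tables that count patients by preferred term may fall less, because a patient can have another related event under the same term.

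**5. What does not depend on relatedness**

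All-cause TEAE tables to day 30, the list of SAEs, the all-SAE summary and the summary of deaths (SAP 6.11.3) are unaffected. Registry output counts an event as serious whether or not it is a TEAE (SAP 6.17).

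**The case against.** The strongest reply is that the protocol sentence is an instruction to the investigator. On that reading the categories are collapsed at data entry: an event the investigator cannot attribute is entered as related, and the SAP's rule loses nothing. The eCRF response list is not in the documents, so this cannot be excluded. It stands as a condition on the point: the loss occurs only if *does not know* is stored as its own value.

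The second reply concerns versions. The supplied protocol was approved in September 2014. The SAP was approved in April 2017 and refers to Amendments (a) and (b), which are not supplied. A later protocol may have moved to three categories, and its section numbers may differ. This also stands. It affects which correction is right, but the SAP would still need to cite its source correctly.

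Three stronger readings are tempting, and the documents do not support them:

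- A reader might infer that both *probably related* and *does not know* events are lost. The SAP's *related* carries the protocol's meaning of *probably related*, so only *does not know* is unmapped.
- A reader might infer that related counts would certainly be too low, by no more than the share of all AEs coded *does not know*. The loss is conditional on storage, the share is not given, and the fall is D/(P+Q+D), which is at least that share.
- A reader might infer that the safety picture as a whole would look better than it is. The main all-cause and serious-event outputs do not use relatedness. The reports listed for the DMC in SAP 6.14.1 include summaries of TEAEs and SAEs and safety-system reports for all patients with SAEs. The same rule applies to both arms of a double-blind trial.

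**Conclusion.** The point holds in a limited form. SAP 6.11.2 states a relatedness rule that conflicts with Protocol 10.3.1 on one category, presents that rule as the protocol's own, and points to a section that does not contain it. If *does not know* is a stored eCRF value, related TEAE and SAE event counts could fall by D/(P+Q+D), and late serious *does not know* events would lose TEAE status while remaining in the SAE outputs. D is unknown and may be zero. Any error runs in one direction, towards fewer related events than the protocol's rule gives. No primary or gated endpoint is touched.

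The conclusion assumes that the supplied protocol's categories still applied when the SAP was approved and that the SAP is programmed as written. It should be corrected because a stated rule is wrong against the protocol and the correction is small; a large distortion has not been shown.

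**What to change.** In SAP 6.11.2:

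1. State that any AE recorded as *does not know* counts as related, as in Protocol 10.3.1, both in the related summaries and in the TEAE definition's clause on serious related events.
2. State how a missing relatedness value is handled.
3. Correct the cross-reference from Protocol Section 8.1.2 to 10.3.1.

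If a later amendment changed the categories, cite that amendment instead and declare the difference in SAP Section 8. Checking the eCRF response list will show whether any *does not know* values can exist.

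The cost is one paragraph of the SAP and one mapping line in the programs. The only downside is that related counts may be slightly higher.

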6.11.3. Deaths

All deaths on study not attributed to study disease by the investigator will be listed along with the reason for death, if known. For those deaths attributed to an AE, the listing will include the PT of the AE. A summary of deaths including reasons for death will be produced.

6.11.4. Clinical Laboratory Evaluation

All relevant hematology and chemistry laboratory values will be graded according to CTCAE Version 4. These calculated grades will be summarized by cycle and maximum post-baseline grade over the entire study.

6.11.5. Vital Signs and Other Physical Findings

Temperature, blood pressure, pulse rate, respiration rate, weight and ECOG PS will be summarized by cycle.

6.11.6. Electrocardiograms

Local electrocardiograms (ECGs) will be summarized by cycle and overall. The summary by cycle will classify patients as having normal or abnormal ECG and summarize AEs identified by ECG within each cycle. The overall summary will classify patients as having an abnormal ECG at any point and summarize all AEs identified by ECG.

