10.3.2. Other Safety Measures

10.3.2.1. Electrocardiograms

For each patient, 12-lead digital ECGs will be collected according to the Study Schedule (Attachment 1). Patients must be supine for approximately 5 to 10 minutes before ECG collection and remain supine but awake during ECG collection. Electrocardiograms may be obtained at additional times, if clinically indicated.

Electrocardiograms will be interpreted by a qualified physician (the investigator or qualified designee) at the site as soon after the time of ECG collection as possible, and ideally while the patient is still present for immediate patient management, should any clinically relevant findings be identified.

After enrollment, if a clinically significant increase in the QT/corrected QT (QTc) interval from baseline, or other clinically significant quantitative or qualitative change from baseline, is present, the investigator will assess the patient for symptoms (for example, palpitations, near syncope, syncope) and to determine if the patient can continue in the study. The investigator or qualified designee is responsible for determining if any change in patient management is needed and must document his/her review of the ECG printed at the time of evaluation.

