	Central hematology	Attachment 2	X	X		х	X		Central hematology labs may be drawn up to 3 days prior to Day 1 of each cycle. Additional local hematology labs may be drawn for treatment adjustment and patient management purposes.
	Central chemistry	Attachment 2	X	X		X	X		Central chemistry labs may be drawn up to 3 days prior to Day 1 of each cycle. Additional local chemistry labs may be drawn for treatment adjustment and patient management purposes.
Lab/ Diagnostic	Pharmacokinetic (PK) sampling	Attachment 7	X	X		X			See Attachment 7 for specific timing
Tests	Pharmacogenetic blood sample	Section 10.4.2.2	X						Draw sample before patient is dosed on C1D1
	Biomarker plasma sample	Section 10.4,2	X	X					Draw sample before patient is dosed on C1D1 and upon arrival at site on C2D1
	Local ECG	Section 10.3.2.1	X	X			X		2 to 4 hours after the LY dose on Cycle 1 Day 1, upon arrival at site on Cycle 2 Day 1, 2 to 4 hours after the LY dose on Cycle 4 Day 1. Patients must be supine for approximately 5 to 10 minutes before ECG collection and remain supine but awake during ECG collection

Protocol I3Y-MC-JPBM			Study Treatment Period						
During Treatr	ment Study Schedule	Cycle / Visit	1 2			3	4-	-X	
		Approximate Visit Duration (days)	28	28	3	28	2	28	
		Relative day within a cycle	1	1	21- 28	1	1	21- 28	
Procedure Category	Procedure	Protocol Reference							Comments
	Tumor measurement (palpable or visible)	Section 10.1.1				X	X		Skin lesions identified at baseline require repeat photographic images on Day 1 of every second cycle beginning with Cycle 3 and continuing through Cycle 19 (inclusive), on Day 1 of every third cycle after Cycle 19, and within 14 days of clinical progression. Photographic images may be taken more frequently based upon the discretion of the investigator or following the identification of new skin lesions post-baseline.

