Attachment 7. Protocol JPBM Electrocardiogram and Pharmacokinetic Sampling Schedule

The schedule for PK sampling is summarized in the table below. The date and exact time of collection for each venous blood sample should be documented on the laboratory requisition.

Pharmacokinetic Sampling Schedule

Cycle(C) and Day(D)	ECG	PK Sample Number	Study Drug Dose	Dosing of anastrozole / letrozole	Sampling Time for ECG and PK from Blood ^a
Baseline (Day -14 to Day -1)	X				Day of visit
C1D1	X	1	X ^b	X^{b}	2-4hrs after NSAI and blinded study drug dosed in clinic
C2D1	X	2	Xc	X°	Upon arrival at site (that is, at least 4 hrs after taking NSAI and blinded study drug doses at home)
C2D1		3			3±0.5 hrs after arrival at site (that is, at least 7±0.5 hrs after taking NSAI and blinded study drug doses at home.
C3D1		4	Xp	X^{b}	Prior to NSAI and blinded study drug doses. Patient is dosed in clinic after sample collection.
C3D1		5			3±0.5hrs after NSAI and blinded study drug dosing in clinic
C4D1	Х		Xb	X ^b	2-4hrs after NSAI and blinded study drug dosing in clinic.
30 Day Follow-Up	X				Day of visit

Abbreviation: hrs = hours; NSAI = nonsteroidal aromatase inhibitor; PK = pharmacokinetic.

- ^a Samples of approximately 4 mL of whole blood will be drawn from at least 150 patients randomized in the study for measurement of study treatment and LY2835219 metabolites concentrations.
- Patient is administered NSAI and study drug doses in clinic. On Cycle 1 Day 1 only, patients should take one single dose of blinded study drug and initiate chronic every 12 hours dosing on Cycle 1 Day 2
- c Patient should take NSAI and study drug doses at home at least 4 hours before arrival at site. The time of NSAI and study drug dose intake must be recorded that day..

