6.1.2. Definitions and Conventions

Study drug refers to abemaciclib or placebo.

Study treatment refers to abemaciclib + NSAID or placebo + NSAID.

The **date of randomization** is the date the patient was randomly assigned to abemaciclib + NSAID arm or placebo + NSAID arm using the interactive web response system (IWRS).

The **date of first dose** is the date of the first dose of study drug or NSAID.

The **baseline value of a safety assessment** is the last value observed prior to the first dose of study drug or NSAID.

The **baseline value of an efficacy assessment** is the last value observed prior to the date of randomization. If a patient's first assessment occurs after randomization but prior to the first dose, this assessment will be used as the baseline.

The **study day of a safety event or assessment** will be calculated as:

- the difference between the date of the event or assessment and the date of first dose plus 1 for all events or assessments occurring on or after the day of first dose. For example, if an event occurs on 08JUN2014 and the date of first dose was 06JUN2014, the study day of the event is 3.

- the difference between the date of the event or assessment and the date of first dose for all events or assessments occurring before the day of first dose. For example, if an event occurs on 05JUN2014 and the date of first dose was 06JUN2014, the study day of the event is -1.

The **study day of an efficacy event or assessment** will be calculated as:

- the difference between the date of the event or assessment and the date of randomization plus 1 for all events or assessments occurring on or after the date of randomization.
- the difference between the date of the event or assessment and the date of randomization for all events or assessments occurring before the date of randomization.

One **month** is defined as 365/12 days.

Unless otherwise noted, **summaries of continuous variables** will include a mean, median, standard deviation, minimum, and maximum.

Unless otherwise noted, **summaries of categorical variables** will include the frequency and percentage (relative to the population being analyzed) of each category.

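### The overall abnormal-ECG classification in SAP 6.11.6 is not limited to post-baseline or new abnormality, and no shift from baseline is planned

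*SAP*

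**What the plan says.** SAP 6.11.6 plans two ECG summaries. By cycle: "The summary by cycle will classify patients as having normal or abnormal ECG and summarize AEs identified by ECG within each cycle". Overall: "The overall summary will classify patients as having an abnormal ECG at any point and summarize all AEs identified by ECG". Neither sentence refers to baseline, to a post-baseline window, to a shift or to a change in QTc.

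Elsewhere the SAP does use such references. Section 6.1.2 states that the baseline of a safety assessment "is the last value observed prior to the first dose of study drug or NSAID". Section 6.11.4 says of laboratory grades: "These calculated grades will be summarized by cycle and maximum post-baseline grade over the entire study".

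The protocol collects what a baseline comparison needs. Attachments 1 and 7 schedule an ECG in the 14 days before Cycle 1 Day 1. On treatment, Attachment 1 places ECGs "2 to 4 hours after the LY dose on Cycle 1 Day 1, upon arrival at site on Cycle 2 Day 1", then again 2 to 4 hours after dosing on Cycle 4 Day 1. A last ECG falls at the 30-day follow-up visit. Protocol 10.3.2.1 tells the investigator to assess the patient "if a clinically significant increase in the QT/corrected QT (QTc) interval from baseline, or other clinically significant quantitative or qualitative change from baseline" is found after enrollment.

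**The concern.** A patient whose ECG was abnormal before the first dose and never changed is classified in the same way as one who was normal and became abnormal on abemaciclib. A patient first found abnormal at the 30-day follow-up visit, off treatment, joins the same count. Protocol 7.2 excludes certain cardiac events in the previous 12 months but does not exclude an abnormal ECG, so some baseline abnormality can be expected.

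Randomization balances pre-existing abnormality between the arms in expectation, so the result is dilution and not bias. It adds a similar number of percentage points to both arms, and the arms look more alike than their rates of new abnormality. Worsening in a patient who was already abnormal does not show at all.

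**Working it through.** The plan states no ECG rate, threshold or power, so there is no figure to reproduce. The check is one of wording, followed by an illustration.

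**Wording.** Set side by side, the laboratory section names a post-baseline window and the ECG section does not. Taken literally, any point covers all five scheduled tracings: baseline, Cycles 1, 2 and 4, and the 30-day follow-up. A second reading is possible. The section opens by saying ECGs are summarized by cycle and overall, and overall could mean the cycle tracings taken together. The SAP does not settle this.

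**Formula.** Let *b* be the proportion abnormal at baseline, *q* the new-onset proportion among patients normal at baseline, and *r* the share of baseline-abnormal patients who are counted as abnormal. Then

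- any-point rate = *r·b* + (1 − *b*)·*q*
- between-arm difference, with *b* and *r* equal in the two arms = (1 − *b*)·(*q*_A − *q*_B)

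On the literal reading the baseline tracing itself counts, so *r* = 1. On the post-baseline reading, *r* = 1 only if every baseline abnormality persists.

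**Inputs.** Arm sizes of 300 and 150 come from Protocol 12.1. The values *b* = 20% to 40%, *q*_A = 15% and *q*_B = 5% are assumptions. Take *r* = 1. The off-treatment tracing is left out of the arithmetic.

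| | *b* = 20% | *b* = 40% |
|---|---|---|
| Abemaciclib, any point | 0.20 + 0.80 × 0.15 = 32% (60 + 36 = 96 of 300) | 0.40 + 0.60 × 0.15 = 49% (120 + 27 = 147 of 300) |
| Placebo, any point | 0.20 + 0.80 × 0.05 = 24% (30 + 6 = 36 of 150) | 0.40 + 0.60 × 0.05 = 43% (60 + 4.5 = 64.5 of 150) |
| Difference | 0.80 × 10 = 8 points | 0.60 × 10 = 6 points |
| Ratio | 32/24 = 1.33 | 49/43 = 1.14 |
| Pre-existing share of the abemaciclib count | 60/96 = 62.5% | 120/147 = 82% |
| New onset among baseline-normal patients | 36/240 = 15% v 6/120 = 5% | 27/180 = 15% v 4.5/90 = 5% |

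The last row keeps the 10-point difference and the ratio of 3.0.

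**Other assumptions.** With new onset of 20% versus 10% and *b* from 10% to 50%, the any-point rates run from 28% versus 19% (ratio 1.47) to 60% versus 55% (ratio 1.09), against a true ratio of 2.0. With *b* = 0 there is no dilution.

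**The case against.** The strongest case on the other side is that ECG safety does not rest on this one classification. Three parts of it stand.

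- The same sentence also summarizes adverse events identified by ECG. Protocol 10.3.1 asks for clinically significant ECG findings that result in a diagnosis to be reported. Once reported as adverse events, they fall under SAP 6.11.2, where a treatment-emergent event must begin after first dose or worsen from a pre-existing grade. That is a baseline-referenced route. It is a partial one, because a change that leads to no diagnosis need not become an adverse event, and 6.11.6 itself does not restrict its summary to treatment-emergent events.
- The by-cycle table gives abnormal prevalence at the on-treatment visits by arm, apart from the follow-up tracing. It does not link a patient to her own baseline, so persistent abnormality dilutes it too.
- Protocol 12.2.12 plans no ECG analysis, so the SAP does not depart from a protocol commitment, and no test of ECG rates is planned. Loss of power would therefore describe a comparison that nobody intends to make.

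A reader might infer more than the documents support:

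- *The any-point classification is the only overall ECG measure, and it counts old abnormality in place of new.* Neither is so. The adverse-event summary sits beside it, and new abnormality is still counted, mixed with old.
- *The ECG schedule exists to measure change from baseline.* The protocol does not say this. Section 10.3.2.1 is an instruction to the investigator on managing a patient, not an analysis objective.
- *The laboratory summary has the same gap.* It does not. Section 6.11.4 is already limited to post-baseline grades, and laboratory abnormalities reported as adverse events have the treatment-emergent reference.

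**Conclusion.** The point holds in a limited form. As written, the overall classification in SAP 6.11.6 mixes pre-existing, on-treatment and off-treatment abnormality, and no planned ECG table relates a patient's tracings to her own baseline. The between-arm difference in new abnormality shrinks by the factor (1 − *b*). Under the assumed rates, 15% versus 5% shows as 32-49% versus 24-43%. Those figures depend on assumed baseline and new-onset rates, on equal baseline abnormality in the two arms, and on baseline abnormality being counted in full, either because the baseline tracing is included or because it persists. If some abnormality resolves and only post-baseline tracings count, both rates are lower and the ratio is less compressed.

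Severity is minor. This is a descriptive safety table, and no primary, gated or tested endpoint depends on it.

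**What to change.** In SAP 6.11.6, replace the any-point classification with a by-arm shift table:

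- rows: baseline ECG status (normal, abnormal), using the safety baseline of SAP 6.1.2;
- columns: whether any on-treatment ECG (Cycles 1, 2 and 4) was abnormal;
- reported rate: new abnormality among patients normal at baseline;
- patients abnormal at baseline kept as their own row and not dropped;
- the 30-day follow-up ECG shown separately.

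The by-cycle table and the summary of adverse events identified by ECG can stay as they are.

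The cost is SAP wording and one extra table from data already scheduled for collection. The new-abnormality rate has a smaller denominator: 240 and 120 patients if 20% are abnormal at baseline, 180 and 90 if 40% are. A normal/abnormal shift table still cannot show worsening within the abnormal category or the size of a QTc change, so it should not be presented as a full change-from-baseline analysis. A shift table of laboratory grades would be an optional addition, not a correction.
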